	Pregnant or breast-feeding, or planning.	Risk of harm to fetus not well established for naltrexone or ketamine
	Opioids: physical dependence or anticipated use in the next 30 days	Naltrexone is an opioid-antagonist
	Unstable psychiatric illness (active psychosis, active suicidality)	Ketamine's dissociative effects could worsen psychiatric decompensation
	Moving from region within 30-days of discharge	Cannot have immediate follow up at SUDS
	Discharge to acute/residential treatment	Cannot have immediate follow up at SUDS
	Involuntary hold	Cannot have immediate follow up at SUDS

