### ***Data Collection***

Data will be primarily collected at four time-points (Table 4). Data will be entered by staff into a REDCap database on tablet computers in the hospital and at SUDS clinic. Data collected at enrollment will primarily be descriptive, including demographics, recent drinking history, readiness to change, and various contributing factors to drinking. Immediately after intervention, vital signs,

symptoms, and acceptability will be recorded. Data collected on post-discharge arrival to SUDS clinic will include most 2' clinical outcomes. We will obtain re-admission rate (1' clinical outcome) through chart review, conducted by research team members at 30-days post-discharge.

Table 4 Patient flow and data collection points

Step	Who	Notes	Data collected – staff entered
Patient identified on consult list	ACS	Quick screen that meets inclusion criteria	
↓			
Addiction consult performed	ACS	Evaluation, withdrawal management, medication (though if patient consents to study, will not be prescribed an addiction medication at discharge), brief therapy, referrals, disease screening/harm reduction	
↓			
Screen, consent, randomization	ACS	Formal screen to identify any exclusion criteria. Simple randomization by algorithm	
 
• E-Consent (should include consent to see records in “care everywhere” – some hospitals require permission – when checking for ED visits and re-admissions)
 
• Screening documentation (inclusion and exclusion criteria)
 
• Alcohol-related admissions in last 12 months (date, location, top 3 diagnoses)
 
• Assigned group
 

↓			
Baseline data, referral to SUDS [data collection point #1]	ToD	ToD collects baseline data first, then performs “biopsychosocial intake” and sets up SUDS appointment within 1 week of discharge.  Discharge date is not always predictable;	
 
• Demographics
 
• Baseline clinical data
 
• Depression symptoms baseline (PHQ9 2 wks)
 
• Drinking History 7-days prior to admission (TLFB)
 
• Readiness to change (SOCRATES-8A)
 
• ACE Questionnaire
 

		ACS to review active hospitalized research participants and contact ToD/update date in RedCap as needed.	
↓			

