30-day chart review [data collection point #4]	Research staff	Should check encounters tab as well as “care everywhere” for Denver Metro region.	
 
Admissions (up to 5) within 30 days of discharge date (date, location, up to top 3 main diagnoses based on documentation available).
 
ED visits (up to 5) within 30 days of discharge date (date, location, up to top 3 main diagnoses based on documentation available).
 
AST, ALT obtained at SUDS f/u (if available)
 
Urine EtG obtained at SUDS f/u (if available)
 

Screening: The addiction consult team will attempt to screen patients meeting the inclusion criteria during inpatient admission. We anticipate 10 patients will meet inclusion criteria weekly. They will be assessed for clear exclusion criteria documented in the chart, and if none are noted the patient will be asked if they would like to join the study and complete the screening. If still no exclusion criteria are met and the patient expresses interest, they will be engaged in informed consent. The primary team will be notified by the addiction medicine team. Each combined process of screening and consent is anticipated to require 15 minutes at the end of a typical consultation. The screening window is anticipated to last 5 months.

Randomization: Patients will undergo a simple randomization algorithm to one of three arms.

Intervention:

- **Arm 1:** Receive a single dose of XR naltrexone (380mg) prior to discharge.
- **Arm 2:** Receive a single infusion of IV ketamine (0.5 mg/kg over 40 minutes) prior to discharge.
- **Arm 3:** No single-dose medication
- *All groups will receive enhanced linkage to care that includes contingency management, initiation of biopsychosocial intake, and appointment scheduling. This aspect alone surpasses the current standard of care.*

Contingency Management: Patients will receive a debit card prior to discharge from the hospital. We will utilize a pre-existing system - ClinCard by Greenphire. Participants will receive \$10 upon completion of baseline data, and \$20 upon completion of follow-up data (at SUDS clinic).

Follow up: Patients will be assigned a follow-up within 7 days of discharge at the outpatient addiction clinic (Denver Health SUDS clinic in pavilion K).

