#### **E. Potential Scientific Problems:**

One potential limitation is the small sample size. As a pilot study, our main aim is to test feasibility. A more robust, precise demonstration of clinical effectiveness will be pursued in a future project with data used from this study to inform sample size estimates as well as timelines.

Secondly, patients may be re-admitted to hospitals that do not show up in our medical record system (Epic). Insurance claims data would be ideal, but at this stage the added value does not justify the costs required for acquisition. Notably, Epic “Care Everywhere” can detect admissions in the University of Colorado Health system (12 hospitals in Colorado), SCL Health (5), and Centura Health (17). This network of hospitals provides high coverage based on our population, many of whom are homeless and located in a small regional geography.

Another potential limitation is a low follow-up rate at SUDS. This is one major reason for including contingency management as part of our enhanced linkage to care. Regardless, the primary quantitative outcome (hospital re-admission) will not require data from SUDS attendance to measure.

Alternative designs were considered but deemed beyond the scope of this proposal:

- “*Double dummy*” *placebos*, which can minimize bias in both researcher and participant. However, this would be personnel and time-intensive, and due to ketamine’s unique psychoactive effect, patients are unlikely to be successfully blinded.
- *2x2 factorial design*, which could gain information on combinations of multiple interventions, but would unnecessarily weaken inferences and complicate statistical analysis due to interactions in this small sample.
- *30-day in-person evaluation*, which would facilitate additional longitudinal measurement. However, we are not confident that enough patients would show up (or be reachable by telephone) to allow for meaningful analysis.

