#### **F. Data Analysis Plan:**

Participants’ demographic and baseline clinical data will be tabulated, and differences between groups will be assessed using a Fisher’s Exact Test for categorical variables and a two-sample t-test for continuous variables. These tests

will help evaluate the effectiveness of randomization. Feasibility outcomes (Aim 1) such as adverse events and acceptability (Likert scale) will be compared for each group using a Fisher's Exact Test and Wilcoxon-Mann-Whitney Test, respectively. Overall recruitment rate and follow-up rate will be tallied at the conclusion of data collection.

For Aim 2, all-cause hospital re-admission within 30-days of discharge will be recorded as a binary outcome. Rates of the two medication intervention groups (XR naltrexone or IV ketamine) will be compared against the group that received enhanced linkage to care alone.

This pilot study may not be sufficiently powered for robust hypothesis testing. By one crude estimate, we could have approximately 80% power to detect a difference between a medication group and the linkage-alone group with about 60 participants assuming a re-admission rate is 25% vs 15%. A larger effect size would increase our power and/or reduce the number of participants required. Regardless, this will provide parameter estimates that can inform a future sample size calculation in a larger effectiveness trial.

For further descriptive purposes, a secondary utilization outcome is risk of 30-day all-cause ED visits. This will be evaluated in a similar manner as hospital re-admissions. Additionally, we are interested in the within-subject difference in readiness-to-change. For those who follow-up, a mean of pre/post differences will be calculated, and a paired t-test will be used to determine if the null hypothesis ( $H_0$ : difference = 0) can be rejected. Drinking behavior will be measured using the Timeline Follow Back method. Binge drinking will be defined as 5+ drinks for men, 4+ for women, and the proportion of binge drinking days since discharge will be calculated for each group. Proportions of positive urine ethyl glucuronide (EtG) will also be tabulated for each group.

Data will be analyzed in SAS.

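### The 30-day chart review is directed to Care Everywhere for the Denver Metro region, a narrower area than the hospital network cited for its coverage and than the all-cause outcome

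*Combined protocol and SAP*

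**What the plan says.** Four places in the combined protocol and SAP bear on this.

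- **Section IV.C, Data Collection, Table 4 (30-day chart review row).** Research staff "Should check encounters tab as well as" Care Everywhere "for Denver Metro region". The same row covers admissions and ED visits. The enrolment row of the table plans e-consent for viewing Care Everywhere records because "some hospitals require permission", and sets no regional limit on that consent.
- **Section IV.E, Potential Scientific Problems.** The plan concedes that "patients may be re-admitted to hospitals that do not show up in our medical record system (Epic"). It answers that Care Everywhere "can detect admissions in the University of Colorado Health system (12 hospitals in Colorado), SCL Health (5), and Centura Health (17"), and concludes: "This network of hospitals provides high coverage based on our population, many of whom are homeless and located in a small regional geography".
- **Section IV.A, Table 1, and Section IV.F, Data Analysis Plan.** The primary clinical outcome is 30-day all-cause re-admission, with no geographic limit. It is analysed as a binary variable, and no category is given for incomplete ascertainment. Of the results, the plan says "this will provide parameter estimates that can inform a future sample size calculation in a larger effectiveness trial".
- **Section IV.B, Table 3.** One exclusion criterion is "Moving from region within 30-days of discharge".

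**The concern.** The search instruction and the coverage argument describe different areas. The argument in Section IV.E is made for the three-system network; the instruction names one metropolitan region. No second source would catch what the search leaves out: claims data are ruled out on cost, and a 30-day in-person evaluation was considered and dropped.

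Because the outcome is binary, a re-admission that is not found is counted as no re-admission. That would lower the estimated proportions and the risk difference, which are among the quantities the pilot is meant to pass to a larger trial. Two staff members could also read the instruction differently and search different areas. Re-admissions at hospitals outside the network are a separate, acknowledged limitation. The part at issue here could be found with the tool already in use.

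**Working it through.** **1. Setting the texts side by side**

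| Item | Area stated |
|---|---|
| Outcome definition (Table 1) | None; all-cause |
| E-consent for Care Everywhere (Table 4) | None |
| Coverage argument (Section IV.E) | Three systems, 12 + 5 + 17 = 34 hospitals (my sum), together with a locally concentrated population |
| Search instruction (Table 4) | Denver Metro region |

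Only the search instruction names the metro region. The documents do not say how many of the 34 hospitals lie outside it.

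**2. The plan's own figure**

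The only design figure for this outcome is in Section IV.F: about 80% power with about 60 participants at 25% vs 15%. It does not reproduce. With 20 per arm (equal allocation assumed) and a 5% level, the pooled-variance normal formula gives 11.9% two-sided and 19.5% one-sided. That is a separate matter which neither supports nor weakens this point. I use only the 25% and 15% rates below.

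**3. What under-capture would do**

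Let m be the share of true re-admissions that the metro search misses, taken as equal in all arms. The documents give no value, so m is an assumption, shown from 0 to 30%. Given the local population, the low end is the more plausible.

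- Observed rate = p × (1 − m).
- Observed risk difference = (0.25 − 0.15) × (1 − m).
- Observed risk ratio = 0.15(1 − m) / 0.25(1 − m) = 0.60 for every m.
- Expected events at N = 60, with 25% in the linkage-alone arm and 15% in each medication arm: 20 × 0.25 + 40 × 0.15 = 5 + 6 = 11. Expected missed = 11m.

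| m | Observed rates | Risk difference (points) | Risk ratio | Missed of 11 events |
|---|---|---|---|---|
| 0 | 25% vs 15% | 10 | 0.60 | 0 |
| 5% | 23.75% vs 14.25% | 9.5 | 0.60 | 0.55 |
| 10% | 22.5% vs 13.5% | 9 | 0.60 | 1.1 |
| 20% | 20% vs 12% | 8 | 0.60 | 2.2 |
| 30% | 17.5% vs 10.5% | 7 | 0.60 | 3.3 |

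**4. Carry-over to a later sample size**

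Per arm, for 80% power at two-sided 5%, with p̄ the mean of the two rates:

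n = [1.96 √(2p̄(1 − p̄)) + 0.842 √(p₁(1 − p₁) + p₂(1 − p₂))]² / (p₁ − p₂)²

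- m = 0: 250 per arm
- m = 5%: 267 per arm
- m = 10%: 285 per arm

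These increases arise only if the later trial takes the pilot's rates uncorrected and m is really that large.

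**The case against.** The strongest reply is that a metro search fits the plan's own reasoning. Section IV.E does not rest on the hospital count alone. It calls coverage high because many patients are homeless and live within a small area, and Table 3 removes people who will leave the region within the follow-up window. On that view the metro region is simply where re-admissions are expected. This stands, and is why the loss is probably small. It does not reconcile the two texts: the description applies to many patients, not all, and someone who has not moved can still be admitted elsewhere in Colorado.

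A reader might infer that staff are told to search the metro region only and to disregard anything else. The documents do not say that. The word only is absent, the encounters tab is also checked, and the Table 4 data field asks for the location of each admission without restricting it. What can be said is that one region is named and no other is.

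A reader might also infer that the comparison between arms is biased. The trial is open-label and chart reviewers are not stated to be blinded, but the same instruction applies to every arm and nothing suggests that misses would differ by arm.

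Finally, sampling error is far larger than the effect considered here. For 5 of 20, the exact 95% interval is about 9% to 49%, against a shift of 1.25 to 2.5 points in the 25% rate when m is 5% to 10%. The plan also already admits some under-capture. Both points stand, and they keep this a minor item.

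**Conclusion.** The point holds as a minor inconsistency in how the primary clinical outcome is ascertained. The search instruction is narrower than both the network cited in its support and the outcome definition. Followed literally, it could code a visible re-admission as no event.

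The size cannot be determined from the documents and may be near zero. The illustrative figures assume equal misses across arms, 20 per arm and the plan's rates of 25% and 15%. On those assumptions, absolute rates and the risk difference shrink by the factor 1 − m, while the risk ratio stays at 0.60. It would go too far to say that re-admissions will be lost, or that the later trial will need 267 to 285 rather than 250 per arm, since the documents do not show that any participant would be re-admitted outside the metro area.

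**What to change.** In the 30-day chart review row of Table 4, replace the metro-region wording with a search of all Care Everywhere-linked sites, done the same way for every participant, under the e-consent already planned. The row also covers ED visits, so that secondary outcome gains as well. Section IV.E can then stay as written.

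Report the outcome as re-admission to a hospital visible in Epic or Care Everywhere, and state that it is a lower bound on all-cause re-admission, so that whoever plans the next trial can allow for under-capture.

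The cost is a few more minutes of chart review for each of 45 to 60 patients. No new data source, consent element or staff is needed. The change should be made before chart review starts.

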### IV. Research Methods

#### A. Outcome Measure(s):

See table 1 for primary and secondary outcomes. In brief, our primary outcomes will be those related to feasibility as well as risk of 30-day all-cause hospital re-admissions. Secondary outcomes include risk of 30-day all-cause emergency department visit,

differences in readiness-to-change, and likelihood of having an alcohol metabolite (EtG) in the urine at follow-up.

*Table 1 Primary and secondary outcomes*

	Study Aim	Description	Instrument(s)
1' feasibility outcomes	1	Recruitment rate (# enrolled / month), follow-up rate, patient acceptability, adverse effects	Chart review, questionnaires
1' clinical outcome	2	Risk of 30-day all-cause hospital re-admissions	Chart review
2' clinical outcomes	2	Risk of 30-day all-cause ED visits	Chart review
	2	Within-subject difference in readiness-to-change 	Questionnaire
	2	Laboratory(+) for alcohol at SUDS	Urine EtG
	2	Percent of binge drinking days  since discharge	Questionnaire

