### C. Study Design and Research Methods

We propose an open-label, pilot feasibility trial (n=45-60), randomizing hospitalized patients to receive XR naltrexone, IV ketamine, or neither prior to hospital discharge, along with enhanced linkage to care. The primary clinical

outcome compared across each of the groups will be 30-day re-admission rates ascertained by chart review (Table 1).

To reduce variability, all participants will undergo a standard addiction consultation that includes behavioral components such as supportive therapy and motivational interviewing. They will also receive enhanced linkage to care (hereon “linkage”) which includes being met by a staff member while in the hospital to begin the clinic intake process and assign a follow-up appointment date. Linkage will also include a contingency management (monetary incentive to follow-up) in their post-hospital transition and receive standard case management and counseling at Substance Use Disorder Services (SUDS) clinic.

ACS team members will identify patients meeting inclusion criteria (Table 2), and – after conducting their usual consultation – approach them about the study. Approximately 900 patients met similar inclusion criteria in 2019 (Query by [name]). After screening for exclusion criteria, informed consent will occur, and initial baseline data will be obtained by “Treatment on Demand” (TOD), a grant-funded team of counselors who are already linking hospitalized patients to addiction care. Consented patients will then be randomized, and the ACS will work with the primary team to order and administer the assigned intervention close to discharge. Meanwhile, a TOD counselor will work to establish a follow-up date within seven days post-discharge. Additional data will be collected immediately after the intervention (for those in one of the two medication groups), at SUDS follow up, and 30-days post-discharge by chart review.

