### ***Medications***

XR naltrexone is produced by Alkermes. Due to the cost (~\$1300 on GoodRx for one dose), we will receive samples from Alkermes in a process that has been pre-arranged between DH inpatient pharmacy and their Colorado-based representative, [name]. We received preliminary approval on 12/3/19 from DH Pharmaceuticals and Therapeutics Committee to use these samples in the hospital for this purpose.

IV ketamine is currently utilized at DH at sub-anesthetic doses for pain control, with guidance from PolicyStat #5253340. Its use in pain management is currently limited to ICU settings and utilizes boluses and infusions titrated to pain. According to discussions with inpatient pharmacy, approval for an infusion dose modeled after randomized trials may be granted for use on floor units with specific contingencies: physician/investigator will be present at bedside during the infusion and nursing staff are educated on the protocol. This was discussed at Denver Health’s Medication Administration Forum (MAF) meeting on 3/5/20.

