Intervention administered [data collection point #2]	RN, ACS	
For 'linkage-alone' group, data to be entered following consult.
 
For NTX group, intervention administered prior to discharge (could be same day as consent). Vitals immediately preceding and 40 min post- injection. Data collected after administration.
 
For KET group, intervention administered prior to discharge (could be same day as consent), though should have no food for at least 3 hours (~50% gastric emptying). Vitals immediately preceding, after completion, and 2 hours following end of intervention.
	
 
Vital signs (HR, BP, O2): linkage-alone group- baseline only, recorded after consult. NTX group- baseline, 40 min after administration. KET group- baseline, end of administration (~40min), 2 hours after end of administration.
 
Most recent AST, ALT
 
UDS-5 data
 
[for KET] Dissociative symptoms (CADSS) after administration (40 min)
 
[for NTX and KET] Acceptability of intervention (10-point Likert) after administration
 
[for NTX and KET] Readiness to change (SOCRATES-8A) after administration (40 min)
 
 
ORDER: CMP (if not already obtained), UDS-5 (if not already obtained)
 
ORDER in discharge orders (outpatient): CMP, UDS-5, urine EtG (if not already ordered)

↓			
Presentation to SUDS, data entered, contingency management reward administered [data collection point #3]	SUDS staff	
Upon presentation, staff to collect study data. After completion, will receive contingency management reward.
 
Then patient to complete standard intake/follow-up visit, if willing.
	
 
Drinking History since discharge (TLFB since discharge)
 
Depression symptoms (PHQ9 modified to read "since discharge.")
 
Readiness to change (SOCRATES-8A)
 
[for KET] Dissociative symptoms (CADSS)
 
Adverse Events (Modified PRISE)
 
Acceptability of intervention (10-point Likert)
 

		Staff to instruct patient to present to the clinic laboratory (e.g. pav G) for CMP after the visit.	
 
Contingency management feedback (10-point Likert, open ended)
 

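### Late index-stay adverse events have no listed field in Table 4 unless the patient attends SUDS, although adverse effects are a primary feasibility outcome (minor)

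*Combined protocol and SAP*

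**What the plan says.** Table 1 (section IV.A) lists the primary feasibility outcomes as "Recruitment rate (# enrolled / month), follow-up rate, patient acceptability, adverse effects". It gives their instruments as a group: "Chart review, questionnaires". The Data Analysis Plan (IV.F) compares adverse events between groups with Fisher's Exact Test and states no denominator.

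The Data Collection text in IV.C says "Data will be primarily collected at four time-points (Table 4". It adds that vital signs, symptoms and acceptability are recorded right after the intervention. Table 4 then specifies:

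- **Point #2, in hospital.** Naltrexone: "Vitals immediately preceding and 40 min post- injection". Ketamine: vitals before, at the end of, and 2 h after the infusion, with a dissociation scale at 40 min. Linkage-alone: one baseline set of vitals.
- **Point #3, on presentation to SUDS.** The Modified PRISE, the only item in the table labelled as adverse events. A metabolic panel is requested after the visit.
- **Point #4, chart review by research staff.** "Admissions (up to 5) within 30 days of discharge date", ED visits over the same period, and AST/ALT and urine EtG if obtained at SUDS.

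Section IV.E names low SUDS attendance as a limitation and notes that re-admission can be measured without it. It says nothing comparable about adverse effects.

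**The concern.** Re-admission, the primary clinical outcome, is read from the chart for everyone. Adverse effects, also primary, are not handled that way. Between the last timed in-hospital check and discharge, a non-attender has no listed field in which an adverse event would be written down. Examples are an allergic reaction (rare, according to Table 5) or a transfer to higher-level care.

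Two things are at stake. Aim 1 uses adverse events to plan a larger trial, so whether an event is counted should depend as little as possible on clinic attendance. And scheduled in-hospital observation differs by arm: longest for ketamine, shorter for naltrexone, baseline only for linkage-alone. A between-arm comparison therefore rests partly on how closely each arm was watched. The direction of any net error is unknown.

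**Working it through.** The plan gives no figure for missed events, so the main check is to place each field on a timeline and ask whether it needs SUDS attendance.

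**1. Coverage by time of event, following Table 4 and the Data Collection text**

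| When the event occurs | Attends SUDS | Does not attend |
|---|---|---|
| Up to the last in-hospital check (drug arms) | Symptoms, vitals; dissociation scale for ketamine | Same |
| After that check, before discharge | Modified PRISE, if recalled | **No listed field** |
| After discharge, with admission or ED visit | Modified PRISE if before the visit; chart review | Chart review |
| After discharge, no admission or ED visit | Modified PRISE if before the visit | No listed field |

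In linkage-alone the second row begins at the baseline vitals. The protocol states no recall period for the Modified PRISE, so even attenders' index-stay events depend on recall. This point concerns the second row.

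**2. Length of the window.** The intervention is planned for shortly before discharge, which suggests hours rather than days. But Table 4 allows dosing on the day of consent, warns that discharge dates cannot always be predicted, and sets no dose-to-discharge limit. The length is unknown.

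**3. How many patients would lack the questionnaire.** The historical attendance in sections II and III reproduces: 2/17 = 11.8% (exact 95% CI 1.5% to 36.4%). Those patients did not have this trial's linkage or incentive, so 50% and 75% are added as assumptions. Non-attenders = N × (1 − attendance):

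| Attendance | N = 45 | N = 60 |
|---|---|---|
| 11.8% | 39.7 | 52.9 |
| 50% | 22.5 | 30 |
| 75% | 11.2 | 15 |

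**4. From non-attenders to missed events.** Expected missed events = non-attenders × q, where q is the chance of an event in the window, taken as unrelated to attendance. The documents give no q. For each percentage point of q (an illustrative unit, not an estimate), the expected number is 39.7 × 0.01 ≈ 0.4 to 52.9 × 0.01 ≈ 0.5 at 11.8% attendance, and 11.2 × 0.01 ≈ 0.1 to 15 × 0.01 = 0.15 at 75%. Unless q is sizeable, the count is small.

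**5. Denominator (a related reporting detail, not a measure of the gap).** Suppose 10 of 20 patients in an arm attend and 4 report an event. Over attenders this is 4/10 = 40% (exact 95% CI 12.2% to 73.8%). Over all randomized it is 4/20 = 20% (5.7% to 43.7%), which treats the 10 non-attenders as event-free. IV.F does not say which would be used.

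**The case against.** The case on the other side is substantial.

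- **In-hospital capture is planned.** Symptoms are to be recorded just after the intervention, whatever happens later at SUDS. For ketamine, the condition discussed for use on floor units was that a "physician/investigator will be present at bedside during the infusion and nursing staff are educated on the protocol". This stands, and it confines the gap to later events. A reader might infer that the plan has no safety data apart from SUDS; the Data Collection text contradicts that.
- **Naltrexone follow-up does not end at 40 min.** A reader might infer this from point #2, but 40 min is only the last in-hospital check. The Modified PRISE and metabolic panel follow at SUDS, and the 30-day review of admissions and ED visits, with diagnoses, needs no attendance.
- **Other capture is not ruled out.** Table 1 names chart review as an instrument, and the four time-points are only where data are mainly collected. The addiction consult service also stays in touch with inpatients: "ACS to review active hospitalized research participants and contact ToD/update date in RedCap as needed". This stands in part. That contact serves to update the discharge date, and the one outcome chart review that is specified has no adverse-event or index-stay item.
- **The window is short.** The plan is to "order and administer the assigned intervention close to discharge". Probably so, though no limit is set.
- **The size is unproven.** A reader might take the historical 88.2% non-attendance (15/17) as the share of adverse events lost. It is not: it would apply only to late index-stay events, whose number is unknown and possibly near zero, and it comes from 17 patients without this trial's incentive.

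**Conclusion.** The gap is real but minor. If staff follow Table 4, an adverse event after the point #2 checks and before discharge is not recorded for a patient who does not attend SUDS. The number of missed events is unknown, because the documents give neither a late in-hospital event rate nor a dose-to-discharge time. The conclusion assumes that Table 4 is the working data form and that any unlisted capture would not be uniform across arms. It does not imply that in-hospital safety monitoring is absent, or that the adverse-event results would be biased in a known direction. It is worth acting on because the outcome is primary and the remedy uses a chart review already planned for every patient.

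**What to change.** In Table 4, point #4, add index-stay adverse events from randomization to discharge for all randomized patients in all three arms: date, before or after the dose (drug arms), and seriousness, including prolonged stay or transfer to higher-level care. Leave the re-admission and ED windows anchored at discharge.

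In IV.F:

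- Report the chart-abstracted events over all randomized patients, with days observed per arm and pre-dose events flagged. Treat the between-arm comparison as descriptive: drug-arm patients must be dosed before they leave and linkage-alone patients need not wait, so observation time may differ.
- Report the Modified PRISE separately over SUDS attenders, with the number attending per arm.
- State that non-attenders' post-discharge events without an admission or ED visit remain uncaptured.

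**Cost.** A few REDCap fields and a few more minutes per chart; no new visits, tests or staff. Abstraction would be unblinded in this open-label trial, and some background events would be counted. With 15 to 20 patients per arm, the Modified PRISE rate could rest on very few: 15 × 0.118 = 1.8 to 20 × 0.118 = 2.4 per arm at the historical attendance, or 7.5 to 10 at an assumed 50%.
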